5.7.6 Tau PET Substudy

There is a single tau PET substudy enrolling subjects from both studies (WN29922/WN39658 Longitudinal Tau PET Substudy). This substudy utilizes [¹⁸F]GTP1 (RO6880276) as tau PET radioligand.

Statistical analyses will be conducted on tau PET Median Standardized Uptake Value Ratios (SUVR) in the following four target regions of interest. In composite target regions, each region is weighted by its own volume.

- A temporal composite target region. This region is composed of (both left and right):
 - anterior and posterior superior temporal gyrus,
 - posterior temporal lobe,
 - fusiform gyrus,
 - middle and inferior temporal gyrus;

- A medial temporal composite region not including the hippocampus, composed of (both left and right):
 - Amygdala,
 - Parahippocampus,
 - Anterior medial and lateral temporal lobe;
- Frontal lobe (both left and right);
- Parietal lobe (both left and right);

The inferior cerebellar grey matter will be used as reference region for the calculation of median SUVRs for all four target regions considered.

All the statistical analyses will be based on the Tau-PET-mITT analysis set (see [Table 2](#)) unless otherwise specified.

5.7.6.1 Summaries of Treatment Group Comparability

Demographics and baseline characteristics (including age, sex, medical history, randomization stratification factors) will be summarized descriptively by treatment arm as assigned for both the Tau-PET-mITT analysis set and the Tau-PET-longitudinal analysis set (see [Table 2](#)) using:

- means, SDs, medians, and ranges for continuous variables
- counts and proportions for categorical variables

5.7.6.2 Definition of the Estimand

The scientific question of interest for the Tau PET substudy is to assess the effect of the intended study treatment on the PD endpoint, change from baseline in tau PET median SUVR at Week 116, in the absence of a substantial impact of the COVID-19 pandemic and as if treatment discontinuation would not have occurred. The same estimand will be considered for all four median SUVRs regions.

The primary Tau PET estimand is thus described by the following attributes:

- **Target Population:**
Early (prodromal to mild) AD population as identified by the inclusion and exclusion criteria, see Sections 4.1.1 and 4.1.2 of the substudy protocols and Sections 4.1.1 and 4.1.2 of the main study protocols
- **Variable:**
Change from baseline to Week 116 in tau PET median SUVR
- **Treatment:**
Prescribed study drug including up-titration to the target dose
- **Population-level summary:**
Difference in variable means between treatment arms
- Intercurrent events

- Substantial reduction in drug exposure due to the COVID-19 pandemic (defined as ≥ 4 missed dose-months)
- Treatment discontinuation due to any reason

Tau PET is listed in the protocol under “Pharmacodynamic Biomarker Objective”. Considering that tau PET aims at estimating the Pharmacodynamic effect of treatment, reporting treatment effect estimated "as if there were no treatment discontinuations and no substantial reduction in exposure due to COVID-19 pandemic" (thus using an hypothetical strategy) addresses the scientific question of interest.

Since there are not individual Tau PET substudies for GRADUATE I and GRADUATE II, but rather a single Tau PET substudy across all patients from GRADUATE I and GRADUATE II, Tau PET will be analyzed at the pooled level of GRADUATE I and GRADUATE II.

5.7.6.3 Main Analytical Approach

An MMRM analysis will be used to estimate the mean change from baseline to Week 116 for each of the median SUVRs defined. The model will include the change from baseline in median SUVR as the dependent variable, while adjusting for treatment arm (as categorical), visit (as categorical), APOE $\epsilon 4$ status (as categorical; carrier vs non-carrier), baseline median SUVR, baseline median SUVR-by-visit, study, study-by-visit and treatment-by-visit interaction. Visit will be treated as the repeated variable within a participant. An unstructured variance-covariance matrix will be applied to model the within-participant errors; in the case of non-convergence, compound symmetry will be used, together with a robust estimator of standard error (“sandwich” estimator).

In line with the estimand definition, data acquired after the ICE “Substantial reduction in drug exposure due to the COVID-19 pandemic” (as defined in [Table 3](#)) or more than 56 days from last dose will be excluded from the analysis and treated as missing for the primary analysis purposes.

There will be no data imputation for missing data. However, the MMRM provides unbiased estimates and valid inference in the presence of missing data, under the MAR (missing at random) assumption. A subgroup analysis by parent study may be also considered in order to derive a study-specific treatment effect.

Based the same MMRM model already described in this section, the change from baseline to week 52 in tau PET will also be reported as supplementary analysis.

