5.7.5.3 Visit Windowing

For amyloid PET assessments, due to the long time between scheduled assessments, time windows based on study days, as defined in [Table 7](#), will be used. Study days are defined based on days on study since the date of the first dose, with the day of the first dose being study day 1.

Table 7 Time Windows for Amyloid PET Assessments

| Visit | Target day | Time window |
|----------|------------|--------------|
| Baseline | 1 | Up to day 35 |
| Week 52 | 365 | 281, 449 |
| Week 116 | 813 | 645, 897 |

For Week 116, the time window will cover the week 104 timepoint as well. In case of more than one assessment within a time window, the assessment with the date closest to the target day is selected. For the combined window of Week 104 and 116, the target day is the Week 116 assessment day.

Because of visit windowing, data collected at an early termination visit will be summarized at the corresponding visit as defined by the time window. For participants who have discontinued treatment early, if a PET scan is performed more than 56 days (early termination visit expected 14 days after last dose, followed by time window per protocol for early termination is ± 42 days) after the date of last dose, the PET scan will not be used for the analysis.

The end of a substudy is defined as the date when all participants enrolled in the substudy have:

1. completed the last required amyloid PET scan (Week 116), or
2. completed an early termination scan, or
3. discontinued from the main study.

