5.7.5.5 Main Analytical Approach

An MMRM will be used to estimate the mean change in Centiloid from baseline to Week 116 within each of the substudies. The model will include the change from baseline in Centiloids as the dependent variable, while adjusting for treatment arm (as categorical), visit (as categorical), APOE ε4 status (as categorical; carrier vs non-carrier), type of tracer (as categorical; Florbetaben vs Flutemetamol), baseline Centiloid, baseline Centiloid-by-visit and treatment-by-visit interaction. Visit will be treated as the repeated variable within a participant. An unstructured variance-covariance matrix will be applied to model the within-participant errors; in the case of non-convergence, compound symmetry will be used, together with a robust estimator of standard error (“sandwich” estimator).

In line with the estimand definition, data acquired after the ICE “Substantial reduction in drug exposure due to the COVID-19 pandemic” (as defined in [Table 3](#)) or more than 56 days from treatment discontinuation will be excluded from the analysis and treated as missing for the primary analysis purposes.

There will be no data imputation for missing data. However, the MMRM provides unbiased estimates and valid inference in the presence of missing data, under the MAR (missing at random) assumption.

The difference in least squares means between active drug and placebo arms at Week 116 will be estimated and presented alongside p-value and the 95% confidence interval for treatment difference. A p-value <0.0001 will be regarded as a statistically significant evidence, irrespective of the results of the other primary/secondary endpoints

(along the lines of the [Haybittle–Peto](#) rule, and thus maintaining the overall type-I error within the study).

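### The tau PET 56-day exclusion is written for every participant, not only for those who discontinued, so it can drop a scan that the tau estimand keeps

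*SAP*

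**What the plan says.** SAP 5.7.6.3 opens the exclusion sentence with "In line with the estimand definition, data acquired after the ICE". It then removes data acquired after the COVID-19 exposure event "or more than 56 days from last dose will be excluded from the analysis and treated as missing". Nothing in that sentence, or in the tau windowing section (5.7.6.4), restricts the 56-day part to participants who stopped treatment.

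The estimand cited is in SAP 5.7.6.2. It lists two intercurrent events: a COVID-19-related loss of 4 or more dose-months, and "Treatment discontinuation due to any reason". Scheduled completion and a temporary dosing hold are not listed.

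The amyloid PET section has the same two events (5.7.5.4) and the same Week 116 window (Tables 7 and 9: target Day 813, Days 645 to 897). There the rule is conditional. SAP 5.7.5.3 begins "For participants who have discontinued treatment early, if a PET scan is performed more than 56 days" after the last dose, and SAP 5.7.5.5 counts from stopping treatment: "or more than 56 days from treatment discontinuation will be excluded from the analysis". SAP 5.7.5.3 also explains the 56 days: "early termination visit expected 14 days after last dose, followed by time window per protocol for early termination is ± 42 days". That derivation concerns an early termination visit.

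**The concern.** The estimand's event is stopping treatment. The analysis rule is triggered by time since a dose, which can also exceed 56 days in someone who has not stopped. Two groups are exposed: completers scanned late, and participants on a hold.

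Holds are part of the protocol. Section 5.1.2 interrupts study drug for symptomatic ARIA-E, or for asymptomatic ARIA-E with a BGTS of 4 or more, while assessments continue. Section 4.1.3 foresees ARIA-E still present at the Week 116 MRI, with the participant remaining in the double-blind period.

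The excluded scans enter an MMRM as missing at random, without imputation, although the cause of the exclusion may be a drug-related event. A participant in both PET substudies could also have a scan kept for amyloid and a tau scan at the same visit dropped.

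**Working it through.** **Inputs.**
- Tau Week 116 target Day 813, window Days 645 to 897; Week 52 target Day 365 (SAP Table 9).
- Last double-blind dose at Week 114, or Week 102 for those who finished before the extension (SAP 1.2).
- One missed Q2W dose counts 0.5 dose-month; the event threshold is 4 dose-months, for COVID-19 reasons only (SAP 5.3.2).
- Open-label dosing starts about 2 weeks after the final efficacy visit (Protocol Appendix 1, Table 5, footnote a).

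**Reproducing the SAP's figures.** Study day = 7 × week + 1 gives 365 for Week 52, 729 for Week 104 and 813 for Week 116. The cut-off is 14 + 42 = 56 days.

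**Applying the tau rule.** Last kept day = last-dose day + 56. Gap = 813 − last-dose day.

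| Last dose | Day | Last kept day | Gap to Day 813 | On-target scan | Q2W doses missed to Week 114 | Dose-months |
|---|---|---|---|---|---|---|
| Week 114 | 799 | 855 | 14 | kept | 0 | 0 |
| Week 108 | 757 | 813 | 56 | kept | 3 | 1.5 |
| Week 106 | 743 | 799 | 70 | dropped | 4 | 2.0 |
| Week 104 | 729 | 785 | 84 | dropped | 5 | 2.5 |
| Week 102 | 715 | 771 | 98 | dropped | 6 | 3.0 |
| Week 100 | 701 | 757 | 112 | dropped | 7 | 3.5 |

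**Completers.** With a Week 114 dose, the unusable days are 856 to 897: 897 − 855 = 42 of the 897 − 813 = 84 days after target. An on-schedule scan falls 14 days after the last dose and is kept. For those who finished before the extension, the Week 104 scan (Day 729) falls 14 days after Day 715 and is also kept.

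**Holds still open at the end.** From Week 106 back to Week 100, the on-target scan is dropped with 2.0 to 3.5 dose-months missed. If the cause is COVID-19, that is below the threshold of 4. If the cause is ARIA-E, the missed doses do not count towards that threshold at all. In neither case has an estimand event occurred.

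**Meaning of last dose.** SAP 5.7.6.3 does not define it. If it means the final double-blind dose, a hold that later resumes loses nothing. If it means the most recent dose before the scan, Week 52 scans are affected too: a dose at Week 44 (Day 309) gives 365 − 309 = 56 days, kept; one at Week 42 (Day 295) gives 70 days, dropped. A hold with a last dose at Week 106 or earlier, still open at the end of double-blind treatment, loses the Week 116 scan under both readings.

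**Open-label drug.** A final visit on Day 813 puts the first open-label dose near Day 827. Table 9 has no cut at that dose; Table 4, for the clinical endpoints, does. In participants who enter the extension, scans on Days 856 to 897 may therefore follow open-label gantenerumab. So may scans between about Day 827 and Day 855, which the present tau rule keeps if last dose means the last double-blind dose.

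**The case against.** The strongest reply is that the sentence is shorthand. It claims to follow the estimand, the only stopping event there is treatment discontinuation, and for someone who has stopped, time from last dose and time from discontinuation are nearly the same. That is a fair guess at intent. It does not settle the point, because a programmer following the tau text would apply the rule to everyone, while the amyloid text shows that the condition can be stated.

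Three stronger readings are tempting, and the documents do not support them.

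- **Completers lose valid on-protocol scans.** The tau visit window is in a substudy protocol not among these documents. Day 855 equals 813 + 42, so if scheduled visits carry the same ±42 days as early termination visits (an assumption), the rule removes only out-of-window scans from completers dosed to Week 114. Nothing shows that any scan fell on Days 856 to 897.
- **About a quarter of the active arm is at risk.** The 26% in Protocol 1.3.2 and 3.3.3 is predicted ARIA-E incidence. Asymptomatic cases with a BGTS below 4 continue dosing, and the share on hold for more than 56 days at a scan is not given. In Study WN25203, new ARIA-E was most frequent at 3 to 6 months and fell substantially after the first year (Protocol 1.2.3). That study used constant doses, so timing under a nine-month titration may differ, but few holds are likely to be open near Week 116.
- **The tau substudy is pooled because it is small, so each loss is costly.** SAP 5.7.6.2 says that it is pooled because it is one substudy across both trials. Small numbers are the reason given for CSF (5.7.7).

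It also stands that this is a biomarker endpoint outside the testing hierarchy in SAP 5.1.

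**Conclusion.** The point holds as a mismatch between the tau exclusion rule and its own estimand. Followed literally, the rule drops an on-target Week 116 scan from a participant who has not discontinued, when a hold remains open after a last dose at Week 106 or earlier. This happens even with fewer than 4 dose-months missed. On-schedule scans of completers are kept.

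The effect is probably small. The documents do not give the number of scans affected, or how many participants were on long holds at a scan. More exclusions on gantenerumab are plausible: in Study WN25203, ARIA-E occurred in 0.8% on placebo and 13.5% on 225 mg. A difference in tau exclusions between arms is therefore an expectation, not a demonstrated result. The day counts assume dosing and visits on schedule.

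**What to change.** In SAP 5.7.6.3:

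- apply the 56-day exclusion only to participants with the treatment-discontinuation intercurrent event;
- define last dose as the last double-blind dose;
- end the Week 116 window in Table 9 at the earlier of Day 897 or the first open-label dose, whether given in this study's extension or in WN42171, as Table 4 already does for the clinical endpoints.

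Use the same sentence in 5.7.5.3 and 5.7.5.5, and the same window end in Table 7. Copying the present amyloid wording alone would not be enough, because it has no cut at the first open-label dose and would keep completer scans to Day 897.

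The cost is one clause in three sections and one entry in two tables, made before unblinding. No new data are needed: the clinical endpoint rules in SAP 5.3.3 already use dates of last dose, withdrawal from treatment and first open-label dose.

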5.7.6.4 Visit Windowing

For tau PET assessments, due to the long time between scheduled assessments, time windows based on study days, as defined in [Table 9](#), will be used. Study days are

defined based on days on study since the date of the first dose, with the day of the first dose being Study Day 1.

Table 9 Time Windows for tau PET Assessments

| Visit | Target study day | Time window |
|----------|------------------|--------------|
| Baseline | 1 | Up to day 35 |
| Week 52 | 365 | 281, 449 |
| Week 116 | 813 | 645, 897 |

5.7.7 Cerebrospinal Fluid (CSF) Analyses

The main analysis for the CSF biomarkers will be based on the pooled dataset of GRADUATE I and GRADUATE II studies (due to the small number of CSF samples within each study). Analyses at individual study level will be conducted as well.

Analysis of CSF biomarkers will be based on the CSF-mITT analysis set unless otherwise specified.

CSF biomarker data will be summarized by treatment group and visit (see schedule of assessment in the study protocol).

For each CSF biomarker, two statistically equivalent ANCOVA models will be considered:

1. *using the change from baseline to Week 116 as dependent variable, with covariates: treatment arm (as categorical), APOE ε4 status (as categorical; carrier vs non-carrier) and baseline biomarker.*
2. *using the value at Week 116 as the dependent variable, with covariates: treatment arm (as categorical), APOE ε4 status (as categorical; carrier vs non-carrier) and baseline biomarker.*

Both models will use log (base 10) transformed biomarker data. The following summary statistics will be estimated after the appropriate back-transformation of the original model parameters:

- The geometric mean at Week 116 for each treatment arm, obtained as 10^{LSM} , where LSM is the least square mean for the corresponding treatment arm based on model 2.
- The geometric mean ratio (gantenerumab relative to placebo) at week 116, obtained as $10^{\text{LSM_GvsP}}$, where LSM_GvsP is the least square means of the contrast of Gantenerumab against placebo based on model 2.
- The %-difference in geometric mean (relative to placebo) at week 116, obtained as $[(10^{\text{LSM_GvsP}}) - 1] * 100$ based on model 2.

- *The %-change from Baseline to Week 116 in the Geometric Mean for each treatment arm, obtained as $[10^{LSM} - 1] * 100$, where LSM is the least square mean for the corresponding treatment arm at the corresponding visit based on model 1*

There will be no data imputation for missing data.

The following CSF biomarkers will be analyzed:

- Total tau (tTau)
- Phosphorylated tau (pTau-181)
- Neurogranin
- Neurofilament light (NFL)

Other exploratory CSF biomarker may be reported separately.

Summaries of Treatment Group Comparability

Demographics and baseline characteristics (including age, sex, medical history, randomization stratification factors) will be summarized descriptively by treatment arm as assigned for both the CSF-mITT analysis set and the CSF-longitudinal analysis set (see [Table 2](#)) using:

- means, SDs, medians, and ranges for continuous variables
- counts and proportions for categorical variables

Visit Windowing

For CSF assessments time windows based on study days, as defined in [Table 10](#), will be used. Study days are defined based on days on study since the date of the first dose, with the day of the first dose being Study Day 1.

Table 10 Time Windows for CSF Assessments

| Visit | Target study day | Time window |
|----------|------------------|--------------|
| Baseline | 1 | Up to day 35 |
| Week 116 | 813 | 645, 897 |

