1.2.1 Treatment Assignment and Blinding

Randomization will be performed centrally using an interactive voice or Web-based response system (IxRS). After screening, participants who meet all eligibility criteria will be randomly assigned to one of two treatment groups (active drug or placebo). The ratio will be 1:1; one active to one placebo. The randomization method will be stratified block-randomization. Randomization to treatment allocation will be stratified by geographic region (Western Europe and Australia vs. Rest of the World vs. North America), participant APOE ϵ 4 status (carrier vs. non-carrier), participant stage of disease (prodromal vs. mild AD), use of AD medication (presence vs. absence), and participation in the longitudinal amyloid and tau PET substudies. Except in circumstances in which a Health Authority, Ethics Committee, or Institutional Review Board requires it, a participant will not be told of his or her APOE ϵ 4 status. Individual participant APOE ϵ 4 genotype results will be blinded to participants, Investigators, and the Sponsor. APOE ϵ 4 status information will be supplied directly to the IxRS vendor by the central testing laboratory so that the information can be incorporated at the time of randomization. For participants for whom APOE ϵ 4 status is already known, the results will be blinded to the Sponsor and, as much as possible, to the site and central MRI reader.

The study is to be conducted in a double-blind manner to minimize potential bias from Investigators and participants. The Sponsor will be blinded to study treatment. In the OLE phase, the Sponsor, participants, and site staff will remain blinded to previous treatment allocation.

The randomization method implemented in the China extension cohort will be the same as that implemented in the global population.

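### The pooled CSF analysis leaves study out of both ANCOVA models, although the SAP's other pooled biomarker model adjusts for it

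*SAP*

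**What the plan says.** SAP 5.7.7 bases the main CSF analysis on GRADUATE I and II combined, "based on the pooled dataset of GRADUATE I and GRADUATE II studies (due to the small number of CSF samples within each study". Two models are specified on log10 data. The first is fitted "using the change from baseline to Week 116 as dependent variable, with covariates: treatment arm (as categorical", and the second "using the value at Week 116 as the dependent variable, with covariates: treatment arm (as categorical". After treatment arm, both lists continue with APOE ε4 status and close at "as categorical; carrier vs non-carrier) and baseline biomarker". Study does not appear, either as a covariate or as a stratum. The same section adds: "Analyses at individual study level will be conducted as well".

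Tau PET is handled differently. SAP 5.7.6.2 states that "Tau PET will be analyzed at the pooled level of GRADUATE I and GRADUATE II", and the model in 5.7.6.3 includes "baseline median SUVR, baseline median SUVR-by-visit, study, study-by-visit and treatment-by-visit interaction". Amyloid PET, plasma and volumetric MRI are each modelled within study (5.7.5.5, 5.7.8, 5.7.9), so tau PET is the only other pooled biomarker model.

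SAP 1.2.1 lists the stratification factors. The last two are "use of AD medication (presence vs. absence), and participation in the longitudinal amyloid and tau PET substudies". Providing CSF is not a factor.

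**The concern.** GRADUATE I and II are separate trials, each randomised 1:1. In the pooled data, study is the unit within which participants were allocated, and the usual course is to carry that unit into the model. The SAP explains why it pools but not why it then ignores study, and its neighbouring pooled analysis does the opposite.

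Two small consequences could follow if baseline-adjusted Week 116 values differ between the trials. The between-study difference would go into the residual and widen the reported standard error. Also, because allocation was not stratified by CSF participation and missing CSF values are not imputed, the mix of studies among participants with Week 116 CSF can differ between arms by chance. That would move the geometric mean ratio slightly. Both come from one mechanism, an unmodelled study difference.

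**Working it through.** **Inputs.** The documents supply the covariate lists, 1:1 allocation and the log10 scale. They give no CSF sample size, SD, completion rate or between-study difference. Assumed: 50, 100 or 200 CSF participants per study, exactly 1:1 within study; 60% with Week 116 CSF (pooled n about 60, 120, 240); baseline SD 0.20 and residual SD 0.08 on log10; slope 0.9; 65% APOE ε4 carriers; no treatment effect. Let *r* be the baseline-adjusted study difference divided by the residual SD.

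**Step 1. The two models behave alike.** On the log scale the change is the value minus baseline, and baseline is a covariate, so the arm contrast and its SE are identical. A numerical check gave differences below 1e-14. The omission affects both equally.

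**Step 2. Large-sample SE.** With half the sample from each study, leaving study out multiplies the SE by sqrt(1 + r²/4):

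- r = 0.25: sqrt(1 + 0.0156) = 1.008
- r = 0.5: sqrt(1 + 0.0625) = 1.031
- r = 1.0: sqrt(1 + 0.25) = 1.118

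**Step 3. Simulation, 4000 runs per cell.** Mean reported SE without study divided by mean reported SE with study:

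| r | n ≈ 60 | n ≈ 120 | n ≈ 240 |
|---|---|---|---|
| 0 | 0.996 | 0.998 | 0.999 |
| 0.25 | 1.004 | 1.006 | 1.007 |
| 0.5 | 1.026 | 1.029 | 1.030 |
| 1.0 (extreme) | 1.117 | 1.117 | 1.118 |

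The first row is the price of an unneeded study term: 0.4%, 0.2% or 0.1% on the SE.

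**Step 4. Error rate and bias.** For r of 0.25 and 0.5, null rejection is 4.5% to 5.2% without study and 4.7% to 5.4% with it (Monte Carlo SE 0.34 points). Mean bias without study is at most 0.006 residual SD. A separate simulation of 200 participants, with 25% missing at random, gave 3.2% without study against 4.9% with it at r = 1.0. The error is therefore towards conservatism.

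**Step 5. Chance imbalance in study mix.** The SD of the between-arm difference in study share is 0.084, 0.058 and 0.042 at the three sample sizes. A typical shift in the contrast is r times that SD:

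- smallest: 0.25 × 0.042 = 0.0105 residual SD; 10^(0.0105 × 0.08) − 1 = 0.19% on the ratio
- largest: 0.5 × 0.084 = 0.042 residual SD; 10^(0.042 × 0.08) − 1 = 0.78% on the ratio

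**Step 6. Sensitivity to exact 1:1 allocation.** The SAP does not guarantee balance inside the CSF subset. With simple random allocation there, the gap SD rises to about 0.13, 0.09 and 0.06, and the cost of an unneeded study term to 0.9%, 0.4% and 0.2%. At n ≈ 60 and r = 0.25 the term is then roughly neutral. At r = 0.5 it still improves the SE by 2% to 3%.

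**The case against.** The strongest reply is that this is a modelling preference. No invalid inference is shown. The trials are described as identical in design, both models already adjust for baseline, and the documents support no particular non-zero study difference. If there is none, adding study makes the SE very slightly worse. That stands, and it sets the low priority.

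The chance shift in Step 5 is also not a second harm. It is sampling variation that the SE without study already covers. Against an SE of about 2/sqrt(n), or 0.26 to 0.13 residual SD, it is about 8% of one SE at r = 0.25 (0.25 × 0.084 / 0.26) and 16% at r = 0.5. That stands too.

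The tau PET precedent has limits. Tau PET is one substudy spanning both trials, whereas CSF is pooled because numbers are small. Nor is the by-study tau PET analysis a firm commitment, while the by-study CSF analysis is. The amyloid PET, tau PET, CSF and plasma models also leave out region, disease stage and AD medication, so short covariate lists are the general style. These points show that the CSF model is not invalid. They do not explain why one pooled model carries study and the other does not. The by-study results leave the pooled main estimate unadjusted, and the SAP specifies no way of combining them.

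**Conclusion.** The point holds as a low-priority improvement. Both pooled CSF models omit study without explanation, and the SAP's only other pooled biomarker model includes it. The effect is a reported SE about 0.4% to 0.7% too large at a between-study difference of 0.25 residual SD and 2.6% to 3.0% at 0.5 SD, with no systematic bias and no inflation of false positives. The 12% at 1.0 SD is an extreme case. Every non-zero difference is an assumption, as are the sample sizes and SDs, so confidence is high that the term is missing and low on how much it matters. CSF is a pharmacodynamic objective outside the fixed testing sequence in SAP 5.1, so no confirmatory conclusion depends on this.

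**What to change.** In SAP 5.7.7, add study (GRADUATE I vs GRADUATE II) as a categorical covariate to the pooled version of both ANCOVA models, in line with 5.7.6.3. Only a main effect is needed, because the CSF models use a single post-baseline visit. State that the individual-study versions keep their present covariates, and make the change before unblinding.

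The cost is one sentence and one degree of freedom, with no new data. If study proves irrelevant, the SE rises by 0.1% to 0.4% under exact 1:1 allocation, or up to about 0.9% at the smallest assumed sample if allocation within the CSF subset is uneven.
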